OAT + PET. In addition to receiving standard buprenorphine- or methadone-maintenance treatment as described above and completing monthly assessments, OAT+PET participants will also receive 12 individual sessions of PET. Beginning in Study Week 1, OAT+PET participants will complete weekly 60-minute PET sessions provided by a doctoral- or master's-level therapist trained in PET. Therapy sessions will be conducted at our research clinic in UHC or remotely via UVM's institutionally supported Zoom platform to reduce the risk of COVID-19 transmission. During Sessions 1-2 and prior to beginning the imaginal and in vivo exposures that are the focus of later PET sessions (Foa et al., 2019), participants will receive education about PTSD, the rationale for PET, and breathing retraining techniques as a method for managing PTSD-associated arousal. During Session 3, participants will work with the therapist to provide an initial description of their traumatic event, develop an exposure hierarchy for in vivo exposures, and the first in vivo exposure exercise will be assigned for homework. Weekly in vivo exposure exercises will be assigned at each subsequent session and involve intentional and gradual exposure to real-life trauma reminders that have been previously avoided but are not inherently harmful. Session 4 will be the first session to include imaginal exposure, in which the participant will describe the traumatic event in detail. Each imaginal exposure will be recorded and participants will be instructed to listen to the recording daily as part of their weekly homework assignment. This process is repeated until the final session, which will also include a review of treatment progress. Although PET sessions will be largely informed by conventional prolonged exposure (Foa et al., 2019), we will make the following modifications to support the effective delivery of PET in a clinical population with concurrent PTSD and OUD and facilitate future dissemination efforts: (a) sessions will be approximately 60 minutes in duration, as 60-minute PET sessions promote similar reductions in PTSD symptoms as the more traditional 90-minute sessions (Nacasch et al., 2015); (b) participants will receive psychoeducation regarding the association between PTSD and SUD symptoms; and (3) participants will complete diaphragmatic breathing at the end of each

imaginal exposure exercise in order to reduce distress to baseline levels.

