OAT + Incentivized PET. Participants randomized to the OAT+PET⁺ condition will receive the procedures noted above for the OAT+PET group plus monetary incentives delivered contingent upon completion of PET sessions. The incentive program will follow the general parameters of the program we developed to promote and sustain abstinence from licit and illicit drugs across a variety of clinical populations (Alessi et al., 2004; Dunn et al., 2008, 2010; Heil et al., 2003, 2004; Higgins et al., 1991, 2004; Roll et al., 1996; Roll & Higgins, 2000; Sigmon et al., 2016). Participants will earn vouchers that have monetary value for attending scheduled PET appointments. Vouchers will be given to participants immediately following completion of each session. No cash will be provided to patients; rather, subjects will be able to submit vouchers to a research assistant in exchange for gift cards that they can use for purchase of retail items and services in the local community. The initial session will be worth \$20. Each consecutive attended session will increase the voucher amount by \$5 such that the 2nd consecutive session will be worth \$25, the 3rd \$30 and so on (Table 1).

To support completion of the full 12-week PET protocol, we will incorporate additional strategically-placed bonuses into the reinforcement schedule with the goal of maximizing the percentage of subjects who complete the full 12-session protocol. Bonuses have been a mainstay of our voucher-based interventions with other challenging populations (Alessi et al., 2004; Dunn et al., 2008, 2010; Higgins et al., 1991; Roll et al., 1996, Roll & Higgins, 2000; Sigmon et al., 2016). First, to support consistent (vs. sporadic) attendance, participants will receive a \$50 bonus for every two consecutive sessions attended (Table 1). Second, to support completion of the full PET protocol, participants will receive a \$100 bonus upon completion of Session 12.

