At each therapy session, participants will complete the PCL-5 (Weathers et al., 2013) and TLFB (Sobell & Sobell, 1996) in order to assess self-reported PTSD symptomatology, opioid use, illicit and licit non-opioid drug use, alcohol use, and access to support services. Therapy sessions may be conducted in-person or remotely via Zoom platform. At 4-, 8-, and 12-weeks post-randomization, all participants will complete follow-up assessments consisting of an abbreviated version of the intake and participants randomized to receive PET will also complete the Working Alliance Inventory Client Form (WAI; Horvath & Greenberg, 1989). A participant satisfaction questionnaire will also be administered at Week 12. Follow-up assessment visits will be conducted in-person at our clinic at UHC. However, study measures may also be administered remotely via phone or Zoom platform. Furthermore, if a participant is at high-risk and/or currently experiencing COVID-19 symptoms, urine collection may be excused and study measures can be administered remotely via phone or Zoom platform. Regardless of experimental group, all participants will receive \$60 for completing the initial intake assessment and \$150 for completing follow-up assessments at 4-, 8-, and 12-weeks post-randomization.

For research involving survey, questionnaires, etc.: Describe the setting and the mode of administering the instrument and the provisions for maintaining privacy and confidentiality. Include the duration, intervals of administration, and overall length of participation.

Not applicable

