Study procedures will be conducted in-person at UVM Substance Abuse Treatment Center or remotely via phone or UVM's institutionally supported Zoom platform. The intake assessment will include the LEC-5 (Weathers et al., 2013), the CAPS-5 (Weathers et al., 2013), PCL-5 (Weathers et al., 2013), Mini International Neuropsychiatric Interview (MINI; Sheehan et al., 1998), Addiction Severity Index (ASI; McLellan et al., 1985), Beck Depression Inventory-II (BDI-II; Beck et al., 1996), Beck Anxiety Inventory (Beck & Steer, 1993), Patient Health Questionnaire - 9 (PHQ-9; Kroenke et al., 2001), Generalized Anxiety Disorder 7-Item Scale (GAD-7; Spitzer et al., 2006), Brief Pain Inventory – Short Form (BPI-SF; Cleeland et al., 1994), The Monetary Choice Questionnaire (MCQ; Kirby et al., 1999), Insomnia Severity Index (ISI; Morin et al., 2011), Credibility/Expectancy Questionnaire (Devilly & Borkovec, 2000), a Demographic and Drug History Questionnaire developed by our group, and a Time Line Follow-Back (TLFB; Sobell & Sobell, 1996) of opioid use, illicit and licit non-opioid drug use, alcohol use, and access to support services. Participants will also provide a urine specimen for immediate onsite testing for opioids (e.g., heroin, methadone, buprenorphine, oxycodone, fentanyl) as well as other, non-opioid drugs (e.g., cocaine, amphetamines, benzodiazepines). Finally, if impairment is suspected, participants may be asked to provide a breath sample. Participants randomized to the OAT+PET and OAT+PET⁺ conditions will complete therapy sessions with research clinicians once per week while receiving PET as described above. Therapy sessions may be conducted in-person or remotely via Zoom platform. At each therapy session, OAT+PET and OAT+PET⁺ participants will complete the PCL-5 (Weathers et al., 2013) and Time Line Follow-Back (TLFB; Sobell & Sobell, 1996) in order to assess self-reported PTSD symptomatology, opioid use, illicit and licit non-opioid drug use, alcohol use, and access to support services. Participants randomized to receive OAT as usual will continue to receive standard buprenorphine or methadone maintenance from their current treatment provider, though all participants will complete follow-up assessments at 4-, 8-, and 12-weeks post-randomization. A participant satisfaction questionnaire will also be administered at Week 12. Follow-up assessment visits will be conducted in-person at our clinic at UHC. However, study measures may also be administered remotely via phone or Zoom platform. Furthermore, if a participant is at high-risk and/or currently experiencing COVID-19 symptoms, urine collection may be excused and study measures can be administered remotely via phone or Zoom platform. Follow-up assessments will consist of an abbreviated version of the intake and participants randomized to receive PET will also complete the Working Alliance Inventory Client Form (WAI; Horvath & Greenberg, 1989).

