Potential Benefits to Participants and Others

Participants may benefit by experiencing reductions in PTSD symptoms during their study participation, including reductions in substance use problems as well as the wide range of medical, psychiatric and psychosocial consequences associated with PTSD. They may also benefit from the financial compensation provided as part of the proposed study. The present study stands to provide scientific benefits by expanding our empirical knowledge related to the mechanisms through which OAT and PET promote reductions in PTSD symptomatology in a highly vulnerable clinical population. Furthermore, by providing PET to individuals with concurrent PTSD and OUD, the proposed research also stands to benefit public health in general by reducing the personal and societal costs associated with PTSD (e.g., medical, psychiatric, and substance use treatment utilization and costs, suicidality, poor physical health and decreased quality of life) in patients with OUD. Overall, the individual participant, the medical and scientific communities, and society in general may benefit by our efforts to determine whether OAT alone may attenuate PTSD symptomatology even in the absence of intensive cognitive-behavioral therapy. As such, the risks to which individuals may be exposed as a function of their research participation are reasonable in relation to the anticipated benefits.

Importance of the Knowledge to be Gained

The proposed project has the potential to produce important new scientific and clinically-relevant information related to the mechanisms through which OAT and PET promote reductions in PTSD symptomatology in a highly vulnerable clinical population. Thus, knowledge gained from this research may significantly improve quality of life, psychiatric distress and psychosocial functioning in this vulnerable population, as well as public health more generally. Consequently, the risk/benefit ratio is favorable. The risks to which individuals are exposed as a consequence of their research participation are generally no more than that associated with continuing opioid treatment as usual. In contrast, the potential and probable benefits to be derived by society in general and by individuals with concurrent PTSD and OUD as a group are considerable. In summary, conducting this research seems well justified.

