Adverse Event, Unanticipated Problem (UAP), Reportable New Information (RNI): Describe how events and UAPs will be evaluated and reported to the IRB. All protocols should specify that, in the absence of more stringent reporting requirements, the guidelines established in the "Adverse Event and Unanticipated Problems Reporting Policy" will be followed. The UVM/UVM Medical Center process for review of adverse events and UAPs to subjects or others should be included in the DSMP.

AEs and SAEs will be assessed at each clinic visit by a trained RA or research therapist. Any SAE will be brought to the attention of the PI as soon as possible and not longer than 24 hrs. Any SAE, whether or not related to study intervention, will be reported to the IRB's CHRBSS using the UVM Adverse Event Reporting Document within 5 days of the event. The CHRBSS will determine whether additional reporting requirements are needed. Any SAEs will also be summarized in the yearly IRB continuing review, including a review of frequency and severity.

Withdrawal Procedures: Define the precise criteria for withdrawing subjects from the study. Include a description of study requirements for when a subject withdraws him or herself from the study (if applicable).

OAT+PET and OAT+PET⁺ participants who miss four consecutive weeks of treatment no longer be eligible to continue in PET but will be eligible to complete follow-up assessments. Furthermore, continued enrollment in standard buprenorphine or methadone maintenance treatment is necessary for patients to continue in PET. Patients who drop out of buprenorphine or methadone maintenance treatment will no longer be eligible for the study and their participation will be terminated. Patients are free not to participate in this study or to withdraw from it at any time. If they decide not to participate in the study, we will be glad to discuss with them other clinically appropriate treatment referrals for PTSD that may be available in Vermont. If patients decide not to participate in this study or to withdraw from this study, their decision will not prejudice their future medical care.

Sources of Materials: Identify sources of research material obtained from individually identifiable human subjects in the form of specimens, records or data. Indicate whether the material or data will be obtained specifically for research purposes or whether use will be made of existing specimens, records or data.

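### AE assessment is tied to an undefined clinic visit, and PET participants are scheduled to be asked up to 15 times against 3 in OAT: cover remote contacts and set a common basis for comparing arms

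*Combined protocol and SAP*

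**What the plan says.** The section on adverse events, unanticipated problems and reportable new information gives the collection rule: "AEs and SAEs will be assessed at each clinic visit by a trained RA or research therapist". The protocol does not define a clinic visit, and it gives no AE question, form or recall period.

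Contacts need not take place in the clinic. Under the OAT + PET condition, "Therapy sessions will be conducted at our research clinic in UHC or remotely via UVM's institutionally supported Zoom platform". Follow-up visits are in person by default, but the section on screening and on-study procedures adds: "However, study measures may also be administered remotely via phone or Zoom platform".

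The number of contacts differs by arm. In the two PET arms:
- "OAT+PET participants will also receive 12 individual sessions of PET", held weekly.
- The incentivized "condition will receive the procedures noted above for the OAT+PET group plus monetary incentives delivered contingent upon completion of PET sessions".

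In all three arms, "all participants will complete follow-up assessments at 4-, 8-, and 12-weeks post-randomization". OAT as usual has no other scheduled study contact after randomization.

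Statistical Considerations does not mention AEs and plans no comparison of them between arms.

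**The concern.** Two features of the rule matter for safety data. First, its wording does not say whether a Zoom session or a phone follow-up counts as an occasion for asking about AEs. Staff could apply it differently from one participant to the next. Second, if AEs are asked about at every contact, PET participants are asked far more often than OAT participants. The incentivized arm would probably be asked more often than the other PET arm, because it is paid to attend.

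Emotional distress during exposure exercises is a named risk under Risks/Benefits. The section on the importance of the knowledge to be gained also makes a comparative statement: "The risks to which individuals are exposed as a consequence of their research participation are generally no more than that associated with continuing opioid treatment". The comparator in that statement is in effect the control condition. Readers of the results will look to the AE data for evidence on that statement. A simple count of all recorded AEs by arm would mix any true difference with a difference in how often people were asked.

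**Working it through.** The documents state no AE rate, no count of AE assessments and no AE comparison, so there is no plan figure to reproduce. The check counts scheduled contacts and then asks how much bias the imbalance could produce.

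**Inputs.** 12 weekly PET sessions in each PET arm; 3 follow-ups (Weeks 4, 8, 12) in every arm; 45 participants per arm. The Purpose section cites mean attendance from an earlier randomized trial of PET in methadone-maintained patients: 7.11 sessions with incentives and 1.80 without.

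**Occasions for asking after randomization.**
- Full attendance, separate follow-ups: (12 + 3) / 3 = 15 / 3 = 5.0.
- Full attendance, follow-ups coinciding with sessions: 12 / 3 = 4.0.
- Separate follow-ups, with attendance as in the cited trial: OAT+PET+ 7.11 + 3 = 10.11, and 10.11 / 3 = 3.4; OAT+PET 1.80 + 3 = 4.80, and 4.80 / 3 = 1.6; OAT 3, ratio 1.

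**From occasions to recorded events (illustrative).** Asking more often does not create events; it catches events that would otherwise be forgotten. Assume that events fall evenly over 12 weeks and that each is reported at the next contact with probability r^(lag in weeks). With contacts every L weeks the share recorded is (1 − r^L) / (−L ln r). The ratio of weekly to 4-weekly asking is then 4(1 − r) / (1 − r^4) = 4 / (1 + r + r² + r³).

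| Weekly recall r | Recorded, weekly | Recorded, 4-weekly | Ratio |
|---|---|---|---|
| 1.00 | 1.000 | 1.000 | 1.00 |
| 0.95 | 0.975 | 0.904 | 1.08 |
| 0.90 | 0.949 | 0.816 | 1.16 |
| 0.80 | 0.896 | 0.661 | 1.36 |
| 0.70 | 0.841 | 0.533 | 1.58 |

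For example, suppose 40% of each arm has one event. At r = 0.90, PET would record 0.40 × 0.949 × 45 = 17.1 participants and OAT 0.40 × 0.816 × 45 = 14.7. At r = 0.70 the figures are 15.1 and 9.6. The model assumes all 12 sessions are attended; with fewer sessions the ratio moves towards 1.

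**Remote contacts (illustrative).** Suppose a share q of contacts is remote, AEs are not asked about there, and contacts are independent. The chance that an OAT participant is never asked is q³: 0.1% at q = 0.10, 1.6% at q = 0.25 and 12.5% at q = 0.50. With 15 PET contacts it is q^15, below 0.01% in each case. The documents give no value for q.

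**After the fix.** Using Weeks 4, 8 and 12 only, the arms have 3, 3 and 3 scheduled assessments, a ratio of 1.0.

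**The case against.** The strongest reply is that the rule excludes nothing. Clinic visit may be meant to include remote visits, and follow-ups are in person by default, so a participant seen only remotely is a limiting case. Other safety routes do not depend on the mode of contact. Under Protection Against Risk, reactions to assessment and treatment are monitored, participants in every condition may call in a crisis, and therapist concern is escalated to the principal investigator. Under Data Safety and Monitoring, staff review participant status and AEs weekly. Closer contact with people undergoing exposure is appropriate, and unequal contact follows from having a usual-care control. Finally, no planned analysis is invalidated, and the risk statement is a prospective justification, not a hypothesis under test.

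Most of this stands. A reader might infer that remote participants are excluded from AE assessment; the documents do not say so, and the point is an ambiguity. A reader might also infer that harms cannot be compared between arms. That is not supported either, because Weeks 4, 8 and 12 are common to all three. Nor should contact ratios of 3.4 or 5 be read as inflation of event rates, since that would require reports to rise in proportion to the number of occasions.

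The reply does not remove the gap. Crisis calls depend on the participant, weekly meetings review events already known, and therapist observation exists only where there is a study therapist. None of these gives the arms equal ascertainment. The rule also permits a research therapist to do the asking; whether this would be the treating therapist is not stated.

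**Conclusion.** The point holds as a gap in the AE collection plan. It is unclear whether AEs are asked about at remote contacts, and scheduled asking is unequal: 5 to 1 at most, 4 to 1 if follow-ups coincide with sessions, and about 3.4, 1.6 and 1 (OAT+PET+, OAT+PET, OAT) if attendance matches the cited trial. A crude table of all recorded AEs would lean towards more events on PET at equal true rates. The illustrative ratio runs from 1.0 to about 1.6 and rests on assumed recall of 100% down to 70% per week with full attendance. Serious AEs should depend less on how often people are asked. Any remote contacts left unasked would add error of unknown size. The matter is worth correcting because the change is cheap and events never asked about may not be recoverable later.

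**What to change.** - In the adverse event section, replace the reference to clinic visits with: at every study contact, in person or remote.
- At Weeks 4, 8 and 12, use one standard AE question in all three arms covering the period since the previous monthly assessment, asked where possible by a research assistant and not by the treating therapist.
- State that any between-arm AE comparison uses those three assessments, and list events first reported at PET sessions separately.

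The cost is one revised sentence, one standard question at assessments that already take place, a few more minutes at remote contacts and one extra table. No visits are added.

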Prolonged Exposure Therapy for PTSD and Opioid Use Disorder

NCT04104022

June 1, 2022

Human Subjects Research Protocol

PROTOCOL SUMMARY

Project Title:

Prolonged Exposure Therapy for PTSD and Opioid Use Disorder

Principal Investigator: [name]

PURPOSE AND OBJECTIVES

Purpose: The importance of the research and the potential knowledge to be gained should be explained in detail. Give background information.

The current U.S. opioid epidemic represents the most devastating public health crisis of our time, with nearly 12 million Americans reporting opioid misuse in 2016 (SAMHSA, 2017). Opioid use disorder (OUD) is associated with a host of adverse consequences including infectious disease, overdoses and premature death, as well as significant economic costs estimated at over \$78 billion annually (Birnbaum et al., 2011; Clausen et al., 2009; Florence et al., 2016; Hser et al., 2001; Jonas et al., 2013; Rudd et al., 2016). Psychiatric comorbidities are prevalent among individuals with OUD with approximately 50% meeting criteria for mood and anxiety disorders (Brooner et al., 1997; Callaly et al., 2001; Gros et al., 2013; Kidorf et al., 2004; Roncero et al., 2016; Strain, 2002). These prevalence rates far exceed those found in the general population (Kessler et al., 2008) and likely confer additive vulnerabilities upon individuals with OUD.

Posttraumatic stress disorder (PTSD) is a chronic and debilitating psychiatric condition that is highly prevalent in this population. Over 90% of individuals with OUD report lifetime trauma exposure, and 33% of these individuals meet criteria for PTSD (Mills et al., 2005, 2006; Pierce et al., 2009). Although opioid agonist treatment (OAT; e.g., methadone, buprenorphine) is the most efficacious treatment for OUD (Mattick et al., 2009, 2014), patients with PTSD generally experience worse treatment outcomes, including continued psychiatric distress, greater treatment dropout, and relapse to illicit opioid use (Ecker et al., 2017; Peirce et al., 2016; Schiff et al., 2010; Teeson et al., 2005; Villagomez et al., 1995).

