For inclusion in the trial, participants must be >18 years old and be currently maintained on methadone or buprenorphine for OUD. They must also endorse >1 traumatic event on the Life Events Checklist for DSM-V (LEC-5; Weathers et al., 2013) and meet current DSM-V PTSD criteria (American Psychiatric Association, 2013) based on the Clinician Administered PTSD Scale for DSM-5 (CAPS-5; Weathers et al., 2013). Participants also must be willing to have therapy sessions audio recorded for the purpose of completing weekly homework assignments and have clear memory for the traumatic event. Consistent with our prior IRB-approved studies among OAT-enrolled patients, eligible participants must be maintained on a stable methadone or buprenorphine dose for >1 month prior to the study (Dunn et al., 2008, 2010; Sigmon et al., 2016ab). At intake, participants will sign a written release to allow study staff to confirm medication dose and clinical stability with the participant's OAT provider.

Individuals with an acute psychotic disorder, bipolar disorder with an active manic episode (but not simply the presence of bipolar disorder), imminent risk for suicide, a medical condition that may interfere with consent or participation (e.g., organic brain syndrome, dementia, head injury, neuropathy, etc.) will be excluded, as well those who demonstrate illiteracy in English. Participants must provide written informed consent to participate. Those meeting the above criteria and interested in the study will be eligible to participate. Individuals who meet the study criteria described above and provide written informed consent will be eligible to participate.

Experimental conditions.

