OAT as usual. Participants randomized to OAT as usual will continue to receive standard buprenorphine or methadone maintenance from their current treatment provider and complete assessments of PTSD symptom severity, psychosocial functioning and drug use at Study Weeks 4, 8, and 12. Follow-up assessment visits will be conducted in-person at our clinic at UHC following all relevant COVID-19-related CDC guidelines and UVM safety protocols. However, study measures may also be administered remotely via phone or UVM's institutionally supported Zoom platform to reduce the risk of COVID-19 transmission. Standard OAT generally includes daily doses of buprenorphine or methadone, medical management, urine toxicology testing, regular attendance at individual or group counseling and case management as needed. As the type and quantity of clinical services received may vary across programs, time and patients, we will administer a TLFB at each study visit specifically assessing the amount and types of services that each participant receives from their OAT provider as well as in the community more generally (e.g., NA/AA support meetings, individual or group counseling, case management).

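### The five-day SAE reporting limit runs from the event, but SAEs are actively sought only at visits, four weeks apart in the OAT arm, and no procedure is stated for non-attenders

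*Combined protocol and SAP*

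**What the plan says.** The section on adverse events, unanticipated problems and reportable new information gives three rules.

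- Finding events: "AEs and SAEs will be assessed at each clinic visit by a trained RA or research therapist".
- Internal escalation: "Any SAE will be brought to the attention of the PI as soon as possible and not longer than 24 hrs". It does not say whether the 24 hours start at the event or when staff learn of it.
- Reporting any SAE, related or not, to the IRB committee: "using the UVM Adverse Event Reporting Document within 5 days of the event". This clock starts at the event.

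Visit frequency differs by arm. Under Experimental conditions, OAT-as-usual participants "complete assessments of PTSD symptom severity, psychosocial functioning and drug use at Study Weeks 4, 8, and 12". In the first PET arm, "OAT+PET participants will complete weekly 60-minute PET sessions", and the incentivized arm follows the same sessions. Follow-up can also be remote: "study measures may also be administered remotely via phone". Whether a remote contact counts as a clinic visit for SAE assessment is not stated.

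Under Withdrawal Procedures, PET participants who miss four weeks in a row lose PET and keep only the follow-up assessments. Anyone who leaves buprenorphine or methadone treatment has participation terminated, and no later safety contact is mentioned. The Participants section provides a link to the treatment provider: at intake, "participants will sign a written release to allow study staff to confirm medication dose and clinical stability with the participant's OAT provider".

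**The concern.** A limit that starts at the event can be kept only if staff hear of the event quickly. With four weeks between scheduled contacts, an SAE may be well past five days old when staff first ask about it. Staff would then breach the protocol through no fault of their own.

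The second issue is completeness. The Purpose section lists "overdoses and premature death" among the consequences of opioid use disorder, so such events are foreseeable here. They are also events that can stop a person attending, and attendance is where SAEs are asked about. If ascertainment depends on attendance, the SAE summary in the yearly continuing review may understate harm. Differences between arms in SAE timing, and possibly in counts, would partly reflect how often staff asked.

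**Working it through.** The plan gives no figure to reproduce. The check sets the reporting limit against the visit spacing.

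**Inputs from the protocol**
- Reporting limit: 5 days from the event (adverse event section).
- OAT arm: assessments at Weeks 4, 8 and 12, a gap of 28 days.
- PET arms: weekly sessions, a gap of 7 days while sessions are attended.

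**Assumptions, not in the documents**
- Onset is uniform over the gap between attended visits.
- The event is learned of only at the next attended visit.
- It is reported to the IRB the same day.

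**Formulas**, for a gap of L days: share found in time = 5/L; greatest lateness = L − 5 days; mean lag from event to visit = L/2.

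| Situation | L (days) | Found within 5 days | Already late | Greatest lateness | Mean lag |
|---|---|---|---|---|---|
| Weekly sessions, all attended | 7 | 5/7 = 71.4% | 28.6% | 2 days | 3.5 days |
| Weekly, one session missed | 14 | 5/14 = 35.7% | 64.3% | 9 days | 7 days |
| Four-weekly, all attended | 28 | 5/28 = 17.9% | 82.1% | 23 days | 14 days |
| Four-weekly, one assessment missed | 56 | 5/56 = 8.9% | 91.1% | 51 days | 28 days |

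Over the 12 weeks (84 days), the OAT arm has three five-day windows that end at a visit: 15/84 = 17.9%, the same answer. If one of the five days goes on escalation to the PI, the shares fall to 4/28 = 14.3% and 4/7 = 57.1%.

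**Who is really seen weekly.** The Purpose section cites a trial of prolonged exposure in methadone patients, with 12 weekly sessions planned. Mean attendance was 1.80 sessions without incentives and 7.11 with them. If attendance here is similar, many OAT+PET participants would move toward the four-weekly row, and the incentivized arm would be observed most often.

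**People outside the schedule.** After a missed Week 12 assessment, no later scheduled contact would reveal an event. After departure from OAT, participation ends, so no later assessment exists. The protocol states no tracing step for either group.

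**The case against.** The strongest reply is that visits are not the only route by which staff may hear of an SAE.

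- Protection Against Risk, item 5, tells participants in every condition that they may call between sessions in a crisis or when distressed.
- Data Safety and Monitoring has active participants' status, and the past week's AEs and SAEs, reviewed at weekly staff meetings.
- Follow-up by phone or Zoom means that missing a clinic visit need not mean no contact.
- OAT retention is an outcome at Weeks 4, 8 and 12, so staff must learn OAT status somehow. Some participants come from the investigators' own opioid treatment program.
- The form's instructions point to an institutional reporting policy, not available here, that may define the clock.

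This stands to a degree, and it rules out several stronger readings.

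- *The deadline cannot be met.* A reader might infer this, but some events fall just before a visit and calls may reveal others.
- *The gravest events will be missed.* That is inference. A non-fatal overdose or an admission can be reported late at the next contact and still be counted. The documents give no rate of death or permanent loss.
- *The provider release is used only at intake.* The text says when it is signed and what it covers; it does not confine its use to intake.
- *The yearly review is the only SAE summary.* The ticks on the monitoring-frequency checklist are not legible in the text available, so a more frequent report cannot be excluded.

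These routes nevertheless do not close the gap. Calls depend on the participant being able and willing to make them. The weekly meetings name no source for events that staff have not heard about. Remote follow-up changes the mode of contact, not the four-week spacing. The release is described for dose and clinical stability, not SAE enquiry.

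The efficacy analyses and power are also unaffected, and Statistical Methods plans no between-arm SAE comparison. That limits the consequence to safety reporting.

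**Conclusion.** The concern holds in a limited form. A five-day limit counted from the event does not fit ascertainment at visits, least of all at four-week spacing. About 18% of SAEs would be found in time with four-weekly visits and about 71% with weekly visits.

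Both figures rest on even onset, an attended next visit, and discovery only there. For people who attend, they are lower bounds, because calls or other contact may bring some events to light sooner. Missed visits push the other way, as the table shows.

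Separately, no procedure is stated for finding hospitalisation, overdose or death in people who miss assessments or leave OAT. SAE counts may therefore be incomplete and may depend on arm and attendance. The documents do not allow the size of that shortfall to be estimated. The change should be made, but it does not threaten the primary analysis.

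**What to change.** 1. In the adverse event section, run both the 24-hour and the five-day limits from the moment any study staff member becomes aware of the SAE. Record the onset date and the awareness date for each event.
2. Word the provider release described under Participants so that it covers SAE enquiries through Week 12.
3. When a participant in any arm misses a Week 4, 8 or 12 assessment and cannot be reached, have existing staff ask the OAT provider about hospitalisation, overdose and death since the last contact.
4. When a participant leaves OAT, attempt a safety contact with the participant and with the last provider. This step is needed because no later assessment would trigger step 3.

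Steps 3 and 4 should follow one written procedure in every arm. Step 1 alone would remove the deadline conflict by wording without finding any more events; steps 2 to 4 affect which SAEs are counted. Weekly versus four-weekly contact would still differ between arms, and the two recorded dates would make that difference visible. No treatment or withdrawal rule changes.

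The cost is revised consent and release wording and occasional calls by existing staff. Some participants may decline the wider release.
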